3	prior to the database lock 20 Jan 2024	Added, in Section 2.1, the plan for multiplicity adjustment for primary and key secondary efficacy objectives – the details of type I error control strategy.	To finalize multiplicity adjustment strategy.
		Edited Section 3, to adjust Efficacy analysis set 2 for Efficacy Estimand.	To redefine the cut-off for different analysis and intercurrent events.
		Edited Section 4.1 to define Baseline and postbaseline observations and related analysis.	Correction.
		Added, in Section 4.2, analysis of time-to-event of interest in disposition.	Amended as per PSAP.
		Edited Section 4.3.3 for sensitivity analysis of primary endpoint and added Section 4.4.1.3 for sensitivity analysis of key secondary endpoints.	To accommodate Regulatory requirements

SAP Version	Approval Date	Change	Rationale
		Added subsections to Section 4.4.2.	For clarification of each supportive secondary endpoints.
		Moved tertiary patient reported outcomes to Section 4.5.3 from Section 4.4.2.3.	Correction.
		Added subsections in 4.5.1 to explicitly mention analysis method for tertiary outcome measures. Methodology for multiple imputations for missing data have been updated.	For clarification.
		Changes were made throughout Section 4.6.2 to align with the PSAP. Added analysis for P-R hypoglycemia and medication error of interest in Section 4.6.2.1 safety topic of interest.	For alignment with PSAP.
		Made subsections to Section 4.6.3.1 (hypoglycemic events) to accommodate analysis from patient reported hypoglycemia and newly added CGM based derived hypoglycemia. Added rule to identify as single hypoglycemia event from the patient reported hypoglycemia events that occurred within 60 minutes to each another. Changed analysis of event rates to accommodate baseline rate instead of baseline incidences in the models.	For clarification.
		Changes were made throughout Sections 4.6.3.2, 4.6.3.3 and 4.6.3.4 and added Section 6.12 to align with the PSAP.	For alignment with PSAP.
		Edited Section 4.7.1 and Section 4.7.2 for clarification and reorganizing of the corresponding analyses. Hence, added Section 6.13 to clarify the interaction effect for subgroup analysis.	For clarification.
		Edited and added texts in Section 6.6 to clarify handling of missing CGM data and definitions of CGM derived hypoglycemic episodes.	For clarification.
		Throughout the SAP made minor changes and reorganization	For clarity, no change to analysis methodologies, so not detailed
4	prior to the database lock	Added sensitivity analysis for primary (in Section 4.4.3) and key secondary analyses (in Section 4.4.1.3) of continuous endpoints to	To comply with FDA's advice.

SAP Version	Approval Date	Change	Rationale		
version		account for potential unequal residual variances			
		with different group sizes.			
		Added treatment regimen analysis for the	To implement FDA's advice.		
		selected secondary and tertiary endpoints (fasting			
		serum glucose, fasting glucose from SMBG, and			
		selected CGM parameters in Sections 4.1 and			
		4.4.2.1.			
		Added missing data at baseline will be imputed	Addition.		
		using MI approach under MAR assumption in			
		Section 4.4.1.			
		Added adjustment for covariates and added	To implement FDA's advice.		
		appropriate baseline covariates for the binary			
		targets in Section 4.5.1.2. Also suggested a			
		missing data imputation for missing			
		hypoglycemia incidence.			
		Added sensitivity analysis that considers all	To implement FDA's feedback		
		hypoglycemic events as one hypoglycemic event	for SAP of the trial I8H-MC-		
		until a succeeding glucose value is \geq 70 mg/dL in	BDCV.		
		Section 4.6.3.1.1.1.			
		Added Section 4.6.4 analysis for device product	According to the new SAP		
		complaints.	template requirement		
		Updated the subgroups for race in Section 4.7.2.	To implement FDA's advice.		
		Clarified definitions of valid CGM period and	To implement FDA's advice.		
		visit; Added sensitivity analysis for selected			
		CGM parameters that derived from all data in			
		Appendix 6.			
		Clarified the SAP language regarding the use	To clarify based on FDA's		
		unplanned measurements for post-baseline	advice.		
		observations for HbA1c analysis in Section 4.1.			
		Also clarified the SAP language for sensitivity			
		analysis in Section 4.3.3.			

Abbreviations: CGM = continuous glucose monitor; FDA = Food and Drug Administration (United States);

PD = pharmacodynamics; PK = pharmacokinetics; P-R = persistent-recurrent; PSAP = program safety analysis plan;

1. Introduction

The study protocol contains a summary of the planned statistical analyses of the most important endpoints, including primary and key secondary endpoints. There are no changes to the analyses described in the protocol. This SAP includes the analyses details for efficacy, safety measures, patient-reported outcomes, and parameters based on continuous glucose-monitoring (CGM). Pharmacokinetic/pharmacodynamics (PK/PD) analyses will be conducted by the PK/PD group and will be described in the PK analysis plan. The specifications for tables, figures and listings will be described in separate documents.

Objectives	Endpoints			
Primary				
 To investigate the hypothesis that LY3209590 is noninferior to the comparator (insulin degludec) on glycemic control in study participants with T2D currently on basal insulin 	• Change from baseline in HbA1c at Week 26			
Key Secondary (Multiplicity Adjusted)				
• To demonstrate LY3209590 is superior to insulin degludec in the selected parameters of glycemic control	 Change from baseline in HbA1c at Week 26 The event rate of participant-reported clinically significant nocturnal hypoglycemia (<54 mg/dL [3.0 mmol/L] or severe) during treatment phase up to Week 78 Time in glucose range between 70 and 180 mg/dL (3.9 and 10.0 mmol/L) inclusive measured during the CGM session prior to Week 26 			
Other Secondary				
To investigate the efficacy of LY3209590 compared with insulin degludec in additional parameters of glycemic control	 Change from baseline in HbA1c at Weeks 52 and 78 Change from baseline in fasting glucose measured by SMBG at Weeks 26, 52, and 78 Glucose variability measured during the CGM session prior to Weeks 26, 52, and 78 Time in glucose range between 70 and 180 mg/dL (3.9 and 10.0 mmol/L) inclusive measured during the CGM session prior to Weeks 52 and 78 Inculin does at Weeks 26, 52, and 78 			
To investigate the safety of LY3209590 compared with insulin degludec	 Incidence and rate of composite of Level 2 and 3 hypoglycemia events during treatment period Body weight change from baseline to Weeks 26, 52, and 78 Time in hypoglycemia with glucose <54 mg/dL (3.0 mmol/L) measured during the CGM session prior to Weeks 26, 52, and 78 Time in hyperglycemia range defined as glucose >180 mg/dL (10.0 mmol/L) measured during the CGM session prior to Weeks 26, 52, and 78 			

1.1. Objectives, Endpoints, and Estimands

Objectives	Endpoints			
• To evaluate treatment impact between LY3209590 and insulin degludec based on patient- reported outcomes questionnaires	 Change from baseline in TRIM-D at Weeks 26, 52, and 78 DTSQ change (DTSQc) from baseline at Weeks 26, 52, and 78 			
Tertiary				
To investigate the treatment impact of LY3209590 compared with insulin degludec on other measures of efficacy, safety, and patient-reported outcomes	 Efficacy: Percentage of participants achieving HbA1c < 7% at Weeks 26, 52, and 78 Percentage of participants achieving HbA1c < 7% at Week 26 without nocturnal hypoglycemia during treatment phase up to Week 26 Percentage of participants achieving HbA1c ≤ 6.5% at Weeks 26, 52, and 78 Change from baseline in fasting serum glucose at Weeks 26, 52, and 78 Safety: Incidence and rate of Level 2 hypoglycemia events during treatment period Incidence and rate of Level 3 hypoglycemia events during treatment period Incidence of positive treatment-emergent antibody of LY3209590 PK/PD: LY3209590 PK and concentration-response relationships to key safety and efficacy measures Potential intrinsic and extrinsic factors Patient-Reported Outcomes: Change from baseline in SIM-Q at Week 26 Frequency of responses to "Basal Insulin Experience: Likelihood of incorporating into routine" at Weeks 26 and 78 Frequency of responses to "Basal Insulin Experience: Preference" at Weeks 26 and 78 Change from baseline in EQ-5D-5L at Weeks 26, 52 and 			
	• Change from baseline in EQ-5D-5L at weeks 26, 52 and 78			

Abbreviations: CGM = continuous glucose monitoring; DTSQc = Diabetes Treatment Satisfaction Questionnaire – Change Version; HbA1c = hemoglobin A1c; SIM-Q = Simplicity Questionnaire; SMBG = self-monitoring of blood glucose; T2D = type 2 diabetes; TRIM-D = Treatment-Related Impact Measure – Diabetes.

Primary Estimand (for primary objective)

US registration

The *primary* clinical question of interest is: What is the treatment difference between LY3209590 and insulin degludec in change from baseline to Week 26 (Visit 22) in HbA1c in study eligible participants with type 2 diabetes (T2D) currently on basal insulin regardless of treatment discontinuation for any reason and regardless of initiation of rescue medication?

The *treatment regimen estimand* will be used for the primary objective and the attributes are described in the following table.

Treatment Regimen Estimand Attribute	Description		
Population	Targeted study population. See Section 3 for details		
Endpoint	HbA1c change from baseline to Week 26.		
Treatment condition	The randomized treatment regardless of treatment		
	discontinuation and use of rescue medications.		
Remaining intercurrent events	None. The 2 intercurrent events, treatment		
	discontinuation for any reason and initiation of rescue		
	medication, are both addressed by the treatment		
	condition of interest attribute.		
Population-level summary	Difference in mean change between treatment		
	conditions.		

Abbreviations: HbA1c = hemoglobin A1c.

Rationale for estimand: The treatment regimen estimand estimates how participants with T2D are treated in clinical practice and takes into account both efficacy and safety.

Registration for other countries

The *primary* clinical question of interest is: What is the treatment difference between LY3209590 and insulin degludec in change from baseline to Week 26 (Visit 22) in HbA1c in study eligible participants with T2D currently on basal insulin and adherence to the randomized treatment without intercurrent events during the study treatment period?

The *efficacy estimand* will be used for the primary objective. This table describes the efficacy estimand attributes.

Efficacy Regimen Estimand Attribute	Description	
Population	Targeted study population. See Section 3 for details	
Endpoint	HbA1c change from baseline to Week 26.	
Treatment condition	The randomized treatment.	
Remaining intercurrent events None. The 2 intercurrent events, treatment		
	discontinuation for any reason and initiation of rescue	
	medication, are both handled by the hypothetical	
	strategy, for example, the potential outcome for those	
	participants if the intercurrent events have not occurred	
	will be estimated.	
Population-level summary	Difference in mean changes between treatment	
	conditions.	

Abbreviations: HbA1c = hemoglobin A1c.

Rationale for estimand: The efficacy estimand supports the interpretation of the treatment effect from participants who adhere to study treatment and are free from the confounding effect of rescue medications.

Secondary Estimands (for multiplicity-adjusted objectives)

The superiority test in change from baseline to Week 26 (Visit 22) in HbA1c will also be based on the primary estimand described above.

The time in glucose range between 70 and 180 mg/dL (3.9 and 10.0 mmol/L) inclusive measured during the CGM session prior to Week 26 (Visit 22) will also use *treatment regimen estimand* for US registration and *efficacy estimand* for other countries.

The participant-reported clinically significant nocturnal hypoglycemia (<54 mg/dL [3.0 mmol/L] or severe) is one of the safety measures for the study. The event rate will be based on all available data during the specific analysis period. Relative rate between randomized treatment groups will be used for treatment comparison.

1.2. Study Design

- Study BDCU is a Phase 3, multicenter, randomized, open-label, comparator-controlled study to evaluate the efficacy and safety of once-weekly basal insulin (LY3209590) compared to insulin degludec in participants with T2D treated with basal insulin.
- The study includes a 3-week screening/lead-in period, a 78-week treatment period, and a 5-week safety follow-up period.
- Participants will continue prior stable diabetes therapy with 0 to 3 allowed non-insulin antihyperglycemic medications during the study.
- Participants will discontinue their previous basal insulin doses at randomization and will be assigned to either LY3209590 or insulin degludec U100.
- Assignment to treatment groups will be determined by an interactive web-response system (IWRS). Participants will be randomly assigned to 1 of the 2 treatment groups in 2:1 ratio (LY3209590 : insulin degludec) at Week 0 (Visit 3). Stratification will be by country, HbA1c stratum at Week -3 (Visit 1) (<8.0%, ≥8.0%), and the type of basal insulin regimen at randomization (a. typical once-daily basal insulin; b. U-300 or BID regimens).
- This is a treat-to-target study, both treatment groups will undergo titration to achieve an FBG target within the range of 80-120 mg/dL. The primary endpoint at Week 26 (Visit 22) is based on participants reaching stable insulin dose by 8 to 12 weeks and glycemic stability in advance of the 26-week primary endpoint Hemoglobin A1c measure.
- Rescue therapy will be considered during the treatment period if the participants meet the protocol criteria of severe, persistent hyperglycemia.
- If study intervention is permanently discontinued, the participant will be encouraged to continue participation in the study for continued monitoring. Both efficacy (including HbA1c) and safety data will continue to be collected per the schedule of activities in the protocol.

2. Statistical Hypotheses

Primary Hypothesis

The primary objective of this study is to test the hypothesis that LY3209590 is noninferior to insulin degludec on glycemic control as measured by change from baseline to Week 26 (Visit 22) in HbA1c in participants with T2D currently on basal insulin. Thus, the null hypothesis (H_{01}) to be tested is the difference in the change from baseline to Week 26 (Visit 22) in HbA1c (LY3209590 – insulin degludec) is greater than the noninferiority margin (NIM). The 2-sided 95% confidence interval (CI) will be used for testing the noninferiority.

Secondary Hypotheses

The key secondary (multiplicity adjusted) objectives are to test the hypotheses that LY3209590 is superior to insulin degludec with respect to:

- change from baseline in HbA1c at Week 26 (Visit 22) H_{02} : the difference (LY3209590 – insulin degludec) ≥ 0.0
- the event rate of clinically significant nocturnal hypoglycemia (<54 mg/dL [3.0 mmol/L] or severe) during treatment period up to Week 78 (Visit 37)

*H*₀₃: the relative event rate (LY3209590 vs. insulin degludec) ≥ 1 

 time in glucose range between 70 and 180 mg/dL (3.9 and 10.0 mmol/L) inclusive measured by CGM collected during the CGM session prior to Week 26 (Visit 22) *H*₀₄: the difference (LY3209590 – insulin degludec) ≤ 0.0

These hypotheses and the primary hypothesis will be tested using a strategy to control the overall type 1 error.

2.1. Multiplicity Adjustment

A graphical approach (Bretz et al. 2009; 2011) for multiple comparisons will be used to ensure the strong control of the overall type I error rate for testing the primary and key secondary (multiplicity adjusted) objectives. The overall significance level (α) will be set to 0.05. The total α will be used for the primary objective first, then the α will be allocated and transitioned to other key secondary objectives once the primary objective is met. Therefore, the noninferiority test for the primary objective will be based on the 2-sided 95% CI. Once the upper limit of the 2-sided 95% CI is below the NIM, the non-inferiority is achieved and the α of 0.05 will be distributed to test superiority for the key secondary objectives. If the p-value of the 2-sided test for one of the key secondary objectives is below the assigned α level, the superiority is demonstrated and the assigned α level will be distributed to the remaining objectives. The iterative test procedure continues until none of the remaining objectives can be demonstrated with their preserved α or all objectives are demonstrated successfully. The NIM of 0.4% (for treatment regimen estimand) and 0.3% (for efficacy estimand) will both be tested to meet different regulatory requirements. No multiplicity adjustments will be made for conducting separate analyses relative to the treatment regimen and efficacy estimands. Each estimand will have its own familywise error rate of 0.05.

For primary and key secondary efficacy objectives, the details of type I error control strategy are illustrated in the figure :

Both treatment regimen estimand and efficacy estimand will be used to assess these objectives. As they are intended for different purposes, no multiplicity adjustments will be made for conducting separate analyses relative to the treatment regimen estimand and efficacy estimands. In addition, no multiplicity adjustments will be made for evaluating other secondary and exploratory objectives, or for safety assessments.

3. Analysis Sets

The following analysis populations and data sets are defined for the purpose of analysis.

Analysis Populations/ Data Sets	Description			
Entered Population	All participants who sign the informed consent form			
Randomized Population	All randomized participants. Participants will be analyzed according to the			
	treatment they were assigned.			
Modified Intent-to-Treat	All randomized participants who took at least 1 dose of study treatment.			
(mITT) Population	Participants will be analyzed according to the treatment they were assigned.			
Efficacy Analysis Set 1 (EAS1)	The data will include:			
for treatment regimen estimand	• mITT Population excluding participants discontinuing the study			
on efficacy measures	treatment due to inadvertent enrollment, and,			
	• all measurements regardless of the use of study treatment or the			
	initiation of rescue medication.			
Efficacy Analysis Set 2 (EAS2)	The data will include:			
for efficacy estimand on	• mITT Population excluding participants discontinuing the study			
efficacy measures	treatment due to inadvertent enrollment, and,			
	• measurements up to the early discontinuation of study treatment or			
	the initiation of rescue medication,			
	The data cutoff for participants who had an intercurrent event is defined by			
	the earliest date from below dates for individual participants except for the analysis on study dose:			
	- the date of last study dose ± 10 days for LY3209590, or ± 1 day for			
	Degludec			
	- the start date of the first rescue medication			
	The data cutoff for analysis on study dose is defined by the earliest date from			
	below dates for individual participants:			
	- the date of last study dose			
	- the start date of the first rescue medication			
Safety Analysis Set (SS)	The data will include:			
	• mITT Population, and,			
	• all measurement regardless of the use of study treatment or the			
	initiation of rescue medication			

4. Statistical Analyses

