	ANCOVA model using treatment, strata	randomization), visit and treatment-by-visit
	(country, and the type of basal insulin at	interaction as fixed effects, and baseline of the
	randomization), and baseline value of the	dependent variable as a covariate. The Kenward-
	dependent variable as independent variables.	Roger approximation will be used to estimate
	The statistical inference will be based on the	denominator degrees of freedom for the MMRM
	multiple imputation framework by Rubin	models. An unstructured covariance structure will
	(1987).	be used to model the within-participant errors. If
		this structure fails to converge, the following
		covariance structures will be used in order until
		one converges:
		1. Toeplitz with heterogeneity
		2. autoregressive with heterogeneity 3.
		compound symmetry with heterogeneous
		variances
		4. Toeplitz
		5. Autoregressive
		6. compound symmetry without heterogeneous
		variances.

Abbreviation: ANCOVA = analysis of covariance; EAS1 = Efficacy Analysis Set 1; EAS2 = Efficacy Analysis Set 2; HbA1c = hemoglobin A1c; MMRM = mixed model repeated measurement.

The 2-sided 95% CI of the LS mean difference (LY3209590 – insulin degludec) in the HbA1c change from baseline to Week 26 (Visit 22) will be estimated. For both estimands, LY3209590 will be declared noninferior to insulin degludec if the upper limit of the 2-side 95% CI for the LS mean difference in the HbA1c (measured in %) change from baseline is below NIM of +0.4%. In addition, the 95% CI for the LS mean difference will be compared to an alternative NIM of +0.3%.

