4.3.3. Sensitivity Analysis

Two-way Tipping Point Analysis

To confirm the robustness of the primary endpoint results in treatment regimen estimand, a 2way tipping point analysis represents varying assumptions for missing data from both treatment groups will be conducted. This sensitivity analysis will focus on missing data at the primary endpoint. Penalties for imputed missing values will be added for both treatment arms. The ANCOVA model for treatment regimen estimand will be conducted after penalties are added. The multiple imputation framework by Rubin (1987) will be used to summarize the results. The corresponding p-values of non-inferiority test will be shown by color scale in the figure.

Imputation under the noninferiority null hypothesis

After imputing the missing data used in the treatment-regimen estimand (Section 4.3.2), imputation under the noninferiority null hypothesis will be conducted by adding 0.4 (NIM) to the same imputed data of LY3209590 group only. The ANCOVA model for treatment regimen estimand will rerun using the adjusted data. The multiple imputation framework by Rubin (1987) will be used to summarize the results.

Including Inadvertently Enrolled Participants

The primary efficacy analysis will be repeated for the mITT population, including participants inadvertently enrolled, for both treatment regimen estimand and efficacy estimand.

Assuming unequal variances due to different group sizes

A sensitivity analysis will be performed on the treatment regimen estimand, using the same ANCOVA model described in Section 4.3.2 but assuming unequal variances to account for potential unequal residual variances due to different group sizes.

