4.4.1.2. Main Analytical Approach

The superiority test in change from baseline to Week 26 (Visit 22) in HbA1c will be based on the same primary endpoint analysis described in Section 4.3.2.

The rate of participant-reported nocturnal hypoglycemia will be analyzed by a negative binomial regression. The analysis details are provided in Section 4.6.3.1.

The time in glucose range between 70 and 180 mg/dL (3.9 and 10.0 mmol/L) inclusive measured by CGM will be analyzed using an ANCOVA model for treatment regimen estimand and an MMRM model for efficacy estimand. The analyses are similar to the primary analysis described in Section 4.3.2 with additional term of baseline HbA1c stratum (<8.0%, $\geq8.0\%$) in analysis models. For treatment regimen estimand, For the treatment-regimen estimand, only participants with an observation either at baseline or at Week 26 (Visit 22) will be included in the analysis. The missing data at baseline will be imputed using multiple imputation with assumption of missing at random and at Week 26 (Visit 22) the missing data will be imputed by multiple imputation with the approach similar to the imputation used for the primary endpoint.

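### For the efficacy estimand, SAP 2.1 sets a 0.3% non-inferiority margin but SAP 4.3.2 declares non-inferiority at 0.4%, so an upper limit from 0.3% to below 0.4% fails one section and passes the other

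*SAP*

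**What the plan says.** SAP 2.1 (Multiplicity Adjustment) gives each estimand its own margin: "The NIM of 0.4% (for treatment regimen estimand) and 0.3% (for efficacy estimand) will both be tested to meet different regulatory requirements". The same section makes the margin the gate to the key secondary tests: "Once the upper limit of the 2-sided 95% CI is below the NIM, the non-inferiority is achieved", after which the 0.05 is distributed. It also gives each estimand its own familywise error rate of 0.05.

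SAP 4.3.2 (Main Analytical Approach) states the decision rule again, without that split. It begins "For both estimands, LY3209590 will be declared noninferior to insulin degludec if the upper limit" of the two-sided 95% interval for the "mean difference in the HbA1c (measured in %) change from baseline is below NIM of +0.4"%. It continues: "In addition, the 95% CI for the LS mean difference will be compared to an alternative NIM of +0.3"%. No estimand, declaration or alpha consequence is attached to that second comparison.

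The other relevant places are:

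- **SAP 2** states the primary null hypothesis against the margin without giving a value.
- **SAP 4.3.3** builds its null imputation on 0.4 ("will be conducted by adding 0.4 (NIM) to the same imputed data of LY3209590 group only"), but only for the treatment regimen estimand.
- **SAP 5** gives power for both margins.
- **Protocol 9.1 and 9.3.2** name both margins as serving different regulatory requirements and do not say which estimand goes with which.

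**The concern.** Both SAP sections are current text, and for the efficacy estimand they give different pass/fail thresholds on the primary endpoint. An upper limit of, say, 0.35% is not below 0.3%, so under 2.1 non-inferiority is not shown and testing in that family stops. The same limit is below 0.4%, so 4.3.2 declares non-inferiority. Read with the gate in 2.1, that declaration releases alpha. If the result fell there, the margin would have to be chosen with the answer in view.

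Two things are at stake in the efficacy family:

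- the primary non-inferiority claim for registration in other countries;
- whether nocturnal hypoglycemia and time in range may be formally tested there.

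Time in range has its own efficacy-estimand analysis (SAP 4.4.1.2: "will be analyzed using an ANCOVA model for treatment regimen estimand and an MMRM model for efficacy estimand"), so its test in that family depends directly on the gate. The nocturnal rate has a single all-data analysis (SAP 1.1: "The event rate will be based on all available data during the specific analysis period") and can still be tested through the treatment regimen family, where both sections gate at 0.4%. HbA1c superiority is not at stake, because it needs an upper limit below 0.

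**Working it through.** **Inputs (SAP 5, matching Protocol 9.5).** 939 randomized 2:1; 15% dropout, leaving 532 and 266 completers (939 × 0.85 = 798.15); SD 1.1%; two-sided 95% interval. True difference 0 for non-inferiority and -0.3% for HbA1c superiority.

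**Standard error and half-width.**
SE = 1.1 × √(1/532 + 1/266) = 0.0826
Half-width = 1.96 × 0.0826 = 0.1619

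**Reproducing the plan's power.** At a true difference of 0, power = Φ((margin − 0.1619)/SE).

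- Margin 0.4%: Φ(2.88) = 99.8% (plan: greater than 99%)
- Margin 0.3%: Φ(1.67) = 95.3% (plan: at least 95%)

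Both stated figures reproduce.

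**The disputed zone.** Both rules need the limit to be below the margin, so the sections disagree when 0.3 ≤ upper limit < 0.4. As point estimates:

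- lower end: 0.3 − 0.1619 = +0.138%
- upper end: 0.4 − 0.1619 = +0.238%

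**Chance of landing there.** For true difference d:
P = Φ((0.4 − 0.1619 − d)/SE) − Φ((0.3 − 0.1619 − d)/SE)

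| True difference d | Source | Below 0.4% | Below 0.3% | Disputed zone |
|---|---|---|---|---|
| -0.30 | plan, superiority | ≈100% | ≈100% | 6 × 10⁻⁸ |
| 0 | plan, non-inferiority | 99.8% | 95.3% | 4.5% |
| +0.05 | assumed here | 98.9% | 85.7% | 13.2% |
| +0.10 | assumed here | 95.3% | 67.8% | 27.5% |
| +0.15 | assumed here | 85.7% | 44.3% | 41.4% |

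**What each section does with the zone, by estimand.**

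| Estimand | SAP 2.1 | SAP 4.3.2 | Conflict |
|---|---|---|---|
| Treatment regimen | 0.4% | 0.4% | none |
| Efficacy | 0.3%: fails, testing stops | 0.4%: non-inferior | yes |

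**The case against.** The strongest counter-reading starts from Protocol 9.3.2. That section applies its rule to both estimands and allows either margin according to regulatory requirement. SAP 4.3.2 largely follows it, and the SAP says the protocol's analyses are unchanged. On that view the parenthetical in 2.1 is the outlier, and 0.3% should not be the automatic default. This has force as a caution about which section to correct, but it does not remove the conflict. Reporting one interval against two margins is harmless; a family with its own 0.05 still needs one margin that opens its gate.

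It is also fair that 4.3.2 contains no alpha-release rule. Release at 0.4% comes from combining its declaration with the gate in 2.1, and 2.1 read alone gives a usable 0.3% gate. But 2.1 releases alpha when non-inferiority is achieved, and 4.3.2 says when it is declared, so a reader has to combine them. The testing figure in 2.1 is not shown in the copy reviewed. It may label the gate, but it could not cancel the sentence in 4.3.2.

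Finally, the practical effect is small on the plan's assumptions. The 4.5% uses an unadjusted SD in completers, while the efficacy analysis adjusts for baseline. With an effective SD of 1.0 or 0.9 (assumed), it falls to about 2% or 0.7%. Time in range also has a treatment regimen analysis. All of this stands and limits the likely damage. It does not make a primary decision rule with two values acceptable.

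**Conclusion.** The concern holds. For the efficacy estimand the SAP gives two thresholds for the primary decision, and neither the protocol nor SAP 5 says which governs. The conflict is confined to that estimand. Type I error is controlled at whichever margin is fixed in advance; the defect is that the text does not fix one.

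The disputed zone is one tenth of a percentage point wide. Its probability is 4.5% at a true difference of 0 and negligible at -0.3%, given SD 1.1% and 532 and 266 completers. It becomes material only if LY3209590 is truly somewhat worse: 13% to 41% for assumed differences of +0.05% to +0.15%. This must be fixed because of what is ambiguous, namely the primary claim and the gate for one registration family. The planning probability alone would not require it.

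**What to change.** Before database lock, reconcile SAP 2.1 and 4.3.2 so that one margin per estimand family both declares non-inferiority and releases alpha. Possible wording for 4.3.2:

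> Non-inferiority is declared, and alpha released, if the upper limit is below +0.4% for the treatment regimen estimand and below +0.3% for the efficacy estimand. Comparison with the other margin is reported but does not release alpha.

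This follows 2.1, the only passage that gives the two estimands different margins, and the sample size already supports 0.3%. The sponsor should confirm the choice against the regulatory requirements, which are not in the documents. If 0.4% is confirmed for the efficacy family, correct 2.1 instead. The testing figure should carry the same margin.

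The cost is one or two SAP sentences. The protocol allows either margin by regulatory requirement and need not change, and neither the data nor the sample size is affected. Keeping 0.3% means a stricter gate for the efficacy family: 95.3% rather than 99.8% power at a true difference of 0.
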